
 Change in SPARCC enthesitis score at Weeks 16, 24, and 52, as compared to baseline in subpopulation with enthesitis (SPARCC > 0) at baseline Change in spinal pain NRS at Weeks 16, 24, and 52, as compared to baseline in subjects reporting spinal pain at baseline Change from baseline in spine pain NRS in those with sacroiliitis on pelvic x-ray at Weeks 16, 24 and 52 Change from baseline in spinal pain NRS in those with investigator assessed spinal involvement at Weeks 16, 24 and 52 Association of investigator assessed sacroiliac involvement with sacroiliitis on x-ray at baseline Proportion of subjects achieving each MDA component (TJC68, SJC66, PASI, BSA, SAPVAS, SGADA, HAQ-DI, tender enthesal points from LEI) at Weeks 16, 24 and 52 Change in quality of life as assessed by SF-36 total score, physical component summary (PCS), and mental component summary (MCS) change from baseline to Weeks 16, 24, and 52 Fatigue as assessed by FACIT-F change from baseline to Weeks 16, 24, and 52 Proportion of subjects achieving ACR50 at Weeks 24 and 52 Proportion of subjects with resolution of enthesitis at Weeks 24 and 52 as 	
 Change in SPARCC enthesitis score at Weeks 16, 24, and 52 Change in spinal pain NRS at Weeks 16, 24, and 52 Change from baseline in spine pain NRS in those with sacroiliitis on pelvic x-ray at Weeks 16, 24 and 52 Change from baseline in spinal pain NRS in those with investigator assessed spinal involvement at Weeks 16, 24 and 52 Clinical and radiographic sacroiliitis Each MDA component (TJC68, SJC66, PASI, BSA, SAPVAS, SGADA, HAQ-DI, tender enthesal points from LEI) at Weeks 16, 24 and 52 Change in SF-36 total score, PCS, and MCS at Weeks 16, 24, and 52 Change in FACIT-F at Weeks 16, 24 and 52 ACR50 at Weeks 24 and 52 Resolution of enthesitis (LEI = 0) at Weeks 24 and 52

Objectives	Endpoints

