8.1.3.7. Investigator Question on Presence of Axial Involvement

The presence of axial involvement will be recorded at baseline.

Investigator will respond Yes/No to the following question: “*Does the subject have axial involvement?*”.

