- Progression of structural damage assessed radiographically and expressed as the change in mTSS at Weeks 16 and 52, compared to baseline
- Change in SPARCC enthesitis score at Weeks 16, 24, and 52, as compared to baseline in subpopulation with enthesitis (SPARCC  $>0$ ) at baseline

- Change in spinal pain NRS at Weeks 16, 24, and 52, as compared to baseline in subjects reporting spinal pain at baseline
- Change from baseline in spine pain NRS in those with sacroiliitis on pelvic x-ray at Weeks 16, 24 and 52
- Change from baseline in spine pain NRS in those with investigator assessed spinal involvement at Weeks 16, 24 and 52
- Association of investigator assessed sacroiliac involvement with sacroiliitis on x-ray
- Proportion of subjects achieving each MDA component (TJC68, SJC66, PASI, BSA, SAPVAS, SGADA, HAQ-DI, tender enthesal points from LEI) at Weeks 16, 24 and 56
- Change in quality of life as assessed by SF-36 total score, physical component summary (PCS), and mental component summary (MCS) change from baseline to Weeks 16, 24, and 52
- Fatigue as assessed by FACIT-F change from baseline to Weeks 16, 24, and 52
- Proportion of subjects achieving ACR50 at Weeks 24 and 52
- Proportion of subjects with resolution of enthesitis at Weeks 24 and 52 as assessed by LEI in subpopulation that had enthesitis (LEI > 0) at baseline
- Proportion of subjects achieving an improvement in PsAID of at least 3 units at Weeks 24 and 52 compared to baseline in subjects with PsAID  $\geq 3$  at baseline
- Proportion of subjects achieving ACR20 at Weeks 24 and 52
- Mean (median) ACR-N at Week 16, where, ACR-N is defined as the largest number N such that ACR-N is met (analogous to the primary endpoint definition of ACR 50)
- Change in enthesitis at Weeks 16, 24 and 52 as assessed by change from baseline in LEI
- Time to resolution of enthesitis at weeks 4, 12 and 16 among subjects with enthesitis (LEI > 0) at baseline
- Occurrence of enthesitis (LEI > 0) at weeks 4, 12 and 16 among subjects without enthesitis (LEI = 0) at baseline
- Depression and anxiety as assessed by change in HADS score from baseline to Weeks 16 and 52
- Change in physical function as assessed by HAQ-DI change from baseline to Weeks 24 and 52
- Proportion of subjects with a decrease of at least 2 from baseline in LEI, among subjects with baseline LEI of at least 2, at weeks 4, 12 and 16
- Subject's Global Impression of Change Questionnaire at weeks 16 and 52

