## 2.6. Exploratory Efficacy Variables

The exploratory efficacy variables of the study are:

- ACR70 at Weeks 16, 24, and 52
- Change in DAS28-CRP at Weeks 16, 24, and 52
- Change in DAPSA at Weeks 16, 24, and 52
- Change in cDAPSA at Weeks 16, 24, and 52
- DAPSA  $\leq 14$  at Weeks 16, 24, and 52
- cDAPSA  $\leq 14$  at Weeks 16, 24, and 52
- DAPSA  $\leq 4$  at Weeks 16, 24, and 52
- cDAPSA  $\leq 4$  at Weeks 16, 24, and 52
- Change in PASDAS at Weeks 16, 24, and 52
- PASI75 at Weeks 16, 24, and 52 in subjects with  $\geq 3\%$  BSA psoriasis at baseline
- PASI90 at Weeks 24 and 52 in subjects with  $\geq 3\%$  BSA psoriasis at baseline
- PASI100 at Weeks 16, 24, and 52 in subjects with  $\geq 3\%$  BSA psoriasis at baseline
- PASI75 at Weeks 16, 24, and 52 in subjects with  $\geq 10\%$  BSA psoriasis at baseline
- PASI90 at Weeks 16, 24 and 52 in subjects with  $\geq 10\%$  BSA psoriasis at baseline
- PASI100 at Weeks 16, 24, and 52 in subjects with  $\geq 10\%$  BSA psoriasis at baseline
- PASI90 at Weeks 16, 24, and 52 in subjects with baseline PASI score  $\geq 10$
- PASI100 at Weeks 16, 24, and 52 in subjects with baseline PASI score  $\geq 10$
- MDA at Weeks 24, and 52
- VLDA at Weeks 16, 24, and 52
- Resolution of dactylitis (LDI=0) at Weeks 16, 24, and 52 in subjects with LDI  $> 0$  at baseline
- Change in mNAPSI at Weeks 16, 24, and 52 in subjects with mNAPSI  $> 0$  at baseline
- Change in mTSS at Weeks 16 and 52
- Change in SPARCC enthesitis score at Weeks 16, 24, and 52 in subjects with SPARCC  $> 0$  at baseline
- Change in spinal pain NRS at Weeks 16, 24, and 52
- Change from baseline in spine pain NRS in those with sacroiliitis on pelvic x-ray at Weeks 16, 24 and 52

- Change from baseline in spine pain NRS in those with investigator assessed spinal involvement at Weeks 16, 24 and 52
- Correlation of investigator assessed spinal involvement with sacroiliitis on x-ray
- Proportion of subjects achieving MDA component (TJC68, SJC66, PASI, BSA, SAPVAS, SGADA, HAQ-DI, tender enthesal points from LEI) at Week 16
- Change in SF-36 total score, physical component summary (PCS), and mental component summary (MCS) at Weeks 16, 24, and 52
- Change in FACIT-F at Weeks 16, 24 and 52
- ACR50 at Weeks 24 and 52
- HAQ-DI change from baseline to Weeks 16, 24 and 52
- Resolution of enthesitis (LEI = 0) at Weeks 24 and 52
- PsAID response at Weeks 24 and 52 in subjects with PsAID  $\geq 3$  at baseline
- ACR20 at Weeks 24 and 52
- ACR-N at week 16

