### **3.2.2. Population of Subjects Targeted by the Clinical Question**

The population of subjects is all randomized males and females  $\geq 18$  years and  $\leq 75$  years with active PsA ( $\geq 3$  SJC66 and  $\geq 3$  TJC68 at screening and baseline visits) as further defined by the inclusion and exclusion criteria.

For some of the secondary endpoints, further restrictions on inclusion in the analysis result in a smaller target population, a subset of the FAS:

- First secondary endpoint: achieving PASI90. This endpoint will be assessed in subjects with  $\geq 3\%$  BSA psoriasis at baseline, to allow for a calculation of PASI90.
- Second secondary endpoint: resolution of enthesitis. This endpoint will be assessed using only subjects with enthesitis at baseline ( $LEI > 0$ ), to ensure this represents improvement in enthesitis rather than having no enthesitis at baseline.
- Sixth secondary endpoint: proportion of subjects achieving an improvement in PsAID of at least 3 units. This endpoint will be assessed using only subjects with PsAID of at least 3 at baseline, to ensure subjects are capable of meeting endpoint, since negative values of PsAID are not possible.

As for the secondary endpoints, further restriction on inclusion in the analysis result in a smaller target population, a subset of the FAS:

- The exploratory endpoint: change from baseline in spine pain NRS. This endpoint will be assessed using only subjects with sacroiliitis at baseline.
- The exploratory endpoint: change from baseline in spine pain NRS. This endpoint will be assessed in those with investigator assessed spinal involvement.
- The exploratory endpoint: time to resolution of enthesitis. This endpoint will be assessed using only subjects with enthesitis at baseline ( $LEI > 0$ ), to ensure this represents improvement in enthesitis rather than having no enthesitis at baseline.
- The exploratory endpoint: occurrence of enthesitis. This endpoint will be assessed using only subjects with enthesitis at baseline ( $LEI = 0$ ), with occurrence defined as of enthesitis ( $LEI > 0$ ) summarized at weeks 4, 8, 12 and 16.

Other secondary and exploratory endpoints will be assessed using the full analysis set. The population being studied represents a population normally seen in clinical practice. This ensures the activity of izokibep can be evaluated across a distribution of disease severity in the study.

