- ACR70 at Weeks 16, 24, and 52
- DAPSA  $\leq 14$  at Weeks 16, 24, and 52
- cDAPSA  $\leq 14$  at Weeks 16, 24, and 52
- DAPSA  $\leq 4$  at Weeks 16, 24, and 52
- cDAPSA  $\leq 4$  at Weeks 16, 24, and 52
- PASI75 at Weeks 16, 24, and 52
- PASI100 at Weeks 16, 24, and 52
- MDA at Weeks 24, and 52
- VLDA at Weeks 16, 24, and 52
- Resolution of dactylitis at Weeks 16, 24, and 52 among those with dactylitis at baseline
- ACR50 at Weeks 24 and 52
- PASI90 at Weeks 24 and 52 among those with  $\geq 3\%$  BSA psoriasis at baseline
- Resolution of enthesitis (LEI = 0) at Weeks 24 and 52 among those with LEI  $> 0$  at baseline
- Resolution of enthesitis (SPARCC = 0) at Weeks 24 and 52 among those with SPARCC  $> 0$  at baseline
- PsAID response at Weeks 24 and 52
- ACR20 at Weeks 24 and 52
- Occurrence of enthesitis (LEI  $> 0$ ) at weeks 4, 8, 12 and 16, among subjects with no enthesitis (LEI = 0) at baseline
- Decrease of at least 2 in LEI, among subjects with baseline LEI of at least 2, at weeks 4, 8, 12 and 16.

The following continuous endpoints will be analyzed at week 16 with an MMRM model as specified in sec 6.6.3, and after week 16 with standard summary statistics for continuous endpoints. LS mean changes and associated SEs with associated 95% CI and p-values will be presented. Models through week 16 will include all data up to Week 16. The following continuous endpoints after Week 16 will be analyzed according to the four randomized treatment groups. Mean changes and associated SEs along with 95% CI according to the four randomized treatment groups will be presented without strata. No p-values will be reported.

- Change from baseline in DAS28-CRP at Weeks 16, 24, and 52
- Change from baseline in DAPSA/cDAPSA at Weeks 16, 24, and 52
- Change from baseline in PASDAS at Weeks 16, 24, and 52

- Change from baseline in mNAPSI at Weeks 16, 24, and 52 in those with nail psoriasis at baseline
- Change from baseline in mTSS at Weeks 16 and 52
- Change from baseline in SPARCC enthesitis score at Weeks 16, 24, and 52 in those with enthesitis at baseline (SPARCC>0)
- Change from baseline in spinal pain NRS at Weeks 16, 24, and 52
- Change from baseline in spine pain NRS in those with sacroiliitis on pelvic x-ray
- Change from baseline in spine pain NRS in those with investigator assessed spinal involvement
- Correlation of investigator assessed spinal involvement with sacroiliitis on x-ray

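### The spinal pain objective covers subjects with spinal pain at baseline, but the endpoint and analysis entries drop that limit, so the reported effect may be diluted

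*SAP*

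**What the plan says.** **Objective.** SAP 2.2.3 reads "Change in spinal pain NRS at Weeks 16, 24, and 52, as compared to baseline in subjects reporting spinal pain at baseline". The objective column of the Protocol (Synopsis and Section 3) uses the same wording.

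**Endpoint and analysis.** The Protocol endpoint column beside that objective carries no population. SAP 2.6 repeats it as "Change in spinal pain NRS at Weeks 16, 24, and 52", and SAP 6.6.5 has "Change from baseline in spinal pain NRS at Weeks 16, 24, and 52".

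**Population rule.** SAP 3.2.2 names endpoints with a narrower population. For spinal pain it names two subsets only: subjects with sacroiliitis, and subjects with investigator-assessed spinal involvement. It then says "Other secondary and exploratory endpoints will be assessed using the full analysis set".

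**Neighbouring entry.** In the same 6.6.5 list, the SPARCC entry keeps its limit: "Change from baseline in SPARCC enthesitis score at Weeks 16, 24, and 52 in those with enthesitis at baseline (SPARCC>0".

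**Association item.** The Protocol objective is "Association of investigator assessed sacroiliac involvement with sacroiliitis on x-ray at baseline". SAP 2.6 and 6.6.5 have "Correlation of investigator assessed spinal involvement with sacroiliitis on x-ray", and 6.6.5 places it among continuous endpoints analysed by the mixed model. The question actually asked (Protocol 8.1.3.7) is a baseline Yes/No: "Does the subject have axial involvement". The pelvic radiograph is also taken at baseline only (Protocol 8.1.3.8).

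**The concern.** A subject who scores 0 on a 0 to 10 pain scale at baseline can stay the same or get worse, but cannot improve. The objective leaves such subjects out. A programmer who follows SAP 6.6.5 and the closing sentence of 3.2.2 would put them in. The reported mean difference would then describe a mixture of subjects with and without spinal pain. It would look smaller than the effect the objective asks about, by a factor that depends on case mix and not on the drug. If the population is left open until the data are seen, the choice is made when it can influence the result.

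The association item has a smaller problem. Two one-time baseline Yes/No items have no change score, so the method heading above the entry does not apply to it and no other method is given.

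**Working it through.** **Step 1. Where the restriction appears.**

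| Place | Limited to spinal pain at baseline? |
|---|---|
| Protocol Synopsis and Section 3, objective column | Yes |
| Protocol Synopsis and Section 3, endpoint column | No |
| SAP 2.2.3, objective | Yes |
| SAP 2.6, variable | No |
| SAP 3.2.2, list of restricted endpoints | Not listed |
| SAP 6.6.5, analysis | No |

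SPARCC is a useful comparison. The Protocol endpoint column omits its restriction too, but SAP 2.6 and 6.6.5 put it back. The mNAPSI and LEI entries in 6.6.5 also state theirs. Spinal pain was not treated the same way.

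**Step 2. Effect on the estimate.** Let p be the share with spinal pain at baseline, D1 the treatment difference among them and D0 the difference among subjects at 0. By randomization p is about equal between arms, so

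full-set difference = p × D1 + (1 − p) × D0.

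If D0 = 0, this is p × D1. The documents give neither p nor D1. With assumed mean changes of −1 on placebo and −2 on izokibep, D1 = −1.0:

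- p = 0.8: 0.8 × (−1.0) = −0.8
- p = 0.6: 0.6 × (−1.0) = −0.6
- p = 0.4: 0.4 × (−1.0) = −0.4

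**Step 3. Effect on power, without baseline adjustment.** Further assumptions: SD 2.5 among subjects with pain, no change in the rest, 100 per arm, two-sided 5% level. The full-set variance in an arm with mean change m is p(SD² + m²) − (pm)².

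At p = 0.6:

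- Restricted set, 60 per arm: SE = 2.5 × √(2/60) = 0.456; 1.0/0.456 = 2.19; power = Φ(2.19 − 1.96) = 59%.
- Full set: placebo variance 0.6 × 7.25 − 0.36 = 3.99; izokibep variance 0.6 × 10.25 − 1.44 = 4.71; SE = √(8.70/100) = 0.295; 0.6/0.295 = 2.03; power = 53%.

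The same steps give 43% against 36% at p = 0.4, and 72% against 68% at p = 0.8.

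**Step 4. Effect on power, with the planned adjustment.** SAP 6.6.3, which 6.6.5 applies to this endpoint, includes the baseline value as a covariate. Step 3 was therefore repeated by simulation as an analysis of covariance at Week 16. Baseline NRS was assumed uniform on 1 to 10 in subjects with pain and 0 otherwise (4,000 runs).

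| Assumption among subjects with pain | p | Restricted | Full set |
|---|---|---|---|
| Change unrelated to baseline | 0.6 | 59% | 57% |
| Change unrelated to baseline | 0.4 | 42% | 39% |
| Change related to baseline (slope 0.4) | 0.6 | 69% | 69% |
| Change related to baseline (slope 0.4) | 0.4 | 50% | 50% |

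A separate run with change unrelated to baseline gave 60% against 58% and 42% against 40%. The power gap is 0 to 3 points. The covariate does not undo Step 2: the adjusted difference still averages over everyone in the model and stays near −0.6 or −0.4.

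**Step 5. Labels.** The Protocol uses sacroiliac involvement for the association and spinal involvement for a subset. The SAP uses sacroiliac in 2.2.3 and spinal in 2.6, 3.2.2 and 6.6.5. Only one investigator item is collected, and it asks about axial involvement.

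**The case against.** **The SAP does not clearly choose the full analysis set.** The list in SAP 3.2.2 is incomplete: it also leaves out the mNAPSI, SPARCC and dactylitis subsets, which are restricted elsewhere. SAP 6.6.5 is partly shorthand, since it lists PASI75, PASI100 and PsAID response without the populations given in 2.6. An omission there need not redefine a population, and 2.2.3 still carries the limit. This stands in part. The text is ambiguous, and inclusion of subjects at 0 is one reading of it. But the reading follows from three entries and the default rule, and nothing in the SAP says that the objective overrides them.

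**The gap does not start in the SAP.** The Protocol endpoint column omits the limit first, and SAP 2.6 copies it. This stands.

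**The power argument is weak.** A reader might infer from the unadjusted figures that the trial loses useful power on this endpoint. The planned model adjusts for baseline, and then most or all of the loss disappears. This stands.

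**The association entry is a stray list item.** A reader might infer that the SAP analyses a different variable, or that the association would really be fitted by the mixed model. Only one investigator item exists, both documents mix the labels, and the entry names its own measure, a correlation. An analyst would probably handle it sensibly. This stands; it is a tidy-up. Kappa would not suit it, because the Protocol asks for association and not agreement.

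**Conclusion.** The concern holds as a mismatch between the objective and the endpoint and analysis entries. If the full analysis set is used, the mean difference shrinks to roughly p times the difference in the intended population: 0.4 to 0.8 of it over the assumed range. This rests on p, which is not given, and on no treatment effect in subjects at 0. Those subjects can still worsen, so if izokibep prevents new spinal pain the dilution is smaller. The documents do not support a claim of material power loss, nor a claim that the SAP has definitely redefined the population.

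The consequence is limited. The endpoint is exploratory, its p-values are descriptive, and none are reported after Week 16. No primary or secondary conclusion and no error-rate control is affected.

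**What to change.** 1. In SAP 2.6 and 6.6.5, add to the spinal pain entry: in subjects with spinal pain at baseline (NRS > 0). List the same restriction in 3.2.2. Neither document defines what counts as reporting spinal pain, so NRS > 0 is a proposal; the sponsor should confirm the cut-off before unblinding.
2. As a minor tidy-up, move the association entry out of the mixed-model list. Report a baseline 2x2 table of the axial-involvement answer by x-ray sacroiliitis, with a measure of association such as an odds ratio or phi and its 95% confidence interval.
3. State once in the SAP that spinal or sacroiliac involvement, as assessed by the investigator, means the collected axial-involvement item.

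The cost is a few lines of SAP text and one small baseline table. No new data are needed. The Protocol objective already carries the restriction, so its endpoint column can be aligned whenever the Protocol is next amended.

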- Mean (median) Area under the curve (AUC) for ACR-N through week 16
- Change from baseline in LEI at Weeks 16, 24 and 52
- Time to first achievement of ACR50

- Time to first achievement of PASI90 among subjects with at least 3% BSA at baseline
- Time to first achievement of MDA
- Time to first achievement of ACR20
- Time to first achievement of PsAID improvement of at least 3 among subjects with PsAID at least 3 at baseline
- Time to first achievement of PASI100 among subjects with at least 3% BSA at baseline
- To investigate whether 1 or both regimens of izokibep (160 mg QW and 160 mg Q2W) are efficacious compared to placebo, in the subpopulation with enthesitis as baseline, as measured by:
  - Proportion of subjects achieving an improvement in PsAID of at least 3 units at Week 16 compared to baseline in subjects with PsAID  $\geq 3$  at baseline
  - Change from baseline in PsAID at Week 16
  - Proportion of subjects with a HAQ-DI decrease of at least 0.35 at Week 16 compared to baseline in subjects with HAQ-DI  $>0.35$  at baseline (Response to HAQ-DI at Week 16)
  - Change in physical function as assessed by HAQ-DI change from baseline to Week 16
  - Proportion of subjects achieving MDA at Week 16
  - Change in DAPSA and cDAPSA at Week 16 as compared to baseline
  - Proportion of subjects achieving VLDA at Week 16
  - Change in quality of life as assessed by SF-36 total score, physical component summary (PCS), and mental component summary (MCS) change from baseline to Weeks 16
  - Proportion of subjects achieving individual MDA components at Week 16 as compared to baseline
- To investigate the relationship between ACR50 response and other factors
  - Association of baseline positive WPI  $\geq 7$  with ACR50 response
- To investigate that the 80 mg Q4W regimen is efficacious compared to placebo, as measured by the same primary, secondary and exploratory endpoints
- To compare the three regimens of izokibep for assessment of dose-response relationships, as measured by the primary and secondary endpoints
- To evaluate the pharmacokinetics of izokibep in subjects with PsA
- To evaluate the immunogenicity of izokibep in subjects with PsA

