- Change from baseline in LEI at Week 16, 24, 52
- Time to resolution of enthesitis at weeks 4, 12 and 16 among subjects with enthesitis (LEI > 0) at baseline
- Occurrence of enthesitis (LEI > 0) at week 4, 12 and 16 among subjects without enthesitis (LEI = 0) at baseline
- HADS change from baseline to Weeks 16 and 52
- Decrease of at least 2 from baseline in LEI, among subjects with baseline LEI of at least 2, at weeks 4, 12 and 16
- Subject's Global Impression of Change Questionnaire at weeks 16 and 52
- AUC for ACR-N through week 16
- Time to first achievement of ACR50
- Time to first achievement of PASI90 among subjects with at least 3% BSA at baseline
- Time to first achievement of MDA
- Time to first achievement of ACR20
- Time to first achievement of PsAID improvement of at least 3 among subjects with PsAID at least 3 at baseline
- Time to first achievement of PASI100 among subjects with at least 3% BSA at baseline
- Trough plasma concentrations of izokibep at collected timepoints
- Presence of anti-drug antibodies (positive or negative)

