- Change from baseline in SF-36 total score, PCS, and MCS at Weeks 16, 24, and 52
- Change from baseline in FACIT-F at Weeks 16, 24, and 52
- Change from baseline in LEI enthesitis score at Weeks 16, 24, and 52 in those with enthesitis at baseline (LEI>0)
- HAQ-DI change from baseline to Weeks 24 and 52
- HADS change from baseline to Week 24 and 52

Change from baseline for the individual components of the ACR and MDA scores will be summarized at Week 16. Summary statistics (n, mean, standard deviation, median, minimum, and maximum) will be provided

- Swollen Joint Count
- Tender Joint Count
- SAPVAS
- SGADA
- IGADA
- HAQ-DI
- CRP
- PASI
- BSA
- Tender enthesal points  $\leq$  1 site out of 6 sites included in LEI

The following will be analyzed with a time to event model, using a log rank test with stratification by the factors used to stratify randomization. Subjects who do not achieve the endpoint at or before the week 16 visit will be censored at the time of the last assessment could be derived at or before week 16.

- Time to resolution of enthesitis (LEI = 0) among subjects with enthesitis (LEI = 0) at baseline.
- Time to first achievement of ACR50

- Time to first achievement of PASI90 among subjects with  $\geq 3\%$  BSA psoriasis at baseline
- Time to first achievement of MDA
- Time to first achievement of ACR20
- Time to first achievement of PsAID improvement of at least 3 among subjects with PsAID  $\geq 3$  at baseline
- Time to first achievement of PASI100 among subjects with PsAID  $\geq 3$  at baseline

WPI will be calculated at baseline. WPI is a scale of 0-19, and is a count of how many of 19 body sites the subject reports pain or tenderness in the prior 7 days. Standard summary statistics for binary data will be calculated by baseline WPI (WPI  $\geq 7$  vs.  $< 7$ ) for the following endpoints:

- ACR50 at week 16 (observed responder, observed non-responder, missing)
- LEI responders at week 16 (observed responder, observed non-responder, missing)
- PsAID at week 16 (observed responder, observed non-responder, missing)
- HAQ-DI at week 16: improvement of at least 0.35 (observed responder, observed non-responder, missing)

Area under the curve (AUC) for ACR-N will be calculated for each subject by triangulating the observed values at baseline (by definition ACR-N = 0 at baseline) and weeks 2, 4, 12 and 16. The area for consecutive visits, using nominal time from Week t and Week u, will be calculated as

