The following subgroups are of interest for summarizing Time to resolution of enthesitis (LEI = 0) among subjects with enthesitis (LEI = 0) at baseline.

- Sex (male, female)
- Prior exposure to TNFi (yes, no)
- LEI score at baseline
  - LEI = 1
  - LEI = 2
  - LEI = 1 or 2
  - LEI  $\geq$  3

The following subgroup is of interest for the endpoints of PASI75, PASI90 and PASI100:

- Baseline BSA 10% or greater

Response rates and difference in response rate will be reported for each subgroup. Cochran-Mantel-Haenszel weighting will be used to calculate a 95% CI for subgroup analyses for each endpoint similar to Section 6.6.1 and 6.6.3 using stratified tests. A forest plot for the difference in response rate and 2-sided 95% CI will also be presented. No p-values will be reported for the subgroup analyses.

PsAID and HAQ-DI response rates will be determined by the proportion of subjects who achieve at least a minimum clinically important difference (MCID) improvement from baseline to Week 16. MCID values are 3 units for PsAID and 0.35 units for HAQ-DI.

Similar to the subgroup analysis above, difference in response rate and 2-sided Cochran-Mantel-Haenszel weighted stratified 95% CI will be reported for subgroup analyses for each binary endpoint.

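### SAP 6.6.5 contradicts the SAP's and protocol's own definitions for three exploratory analyses: time to enthesitis resolution, time to PASI100, and HADS change

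*SAP*

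**What the plan says.** SAP 6.6.5 lists the exploratory endpoints under the method to be used for each.

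- **Enthesitis.** Under the stratified log-rank analyses it has "Time to resolution of enthesitis (LEI = 0) among subjects with enthesitis (LEI = 0) at baseline". SAP 6.6.6 repeats the baseline condition in the sentence that begins "The following subgroups are of interest for summarizing Time to resolution of enthesitis", and then names subgroups with a baseline LEI of 1, 2, 1 or 2, and 3 or more. SAP 2.6 defines the endpoint as "Time to resolution of enthesitis at weeks 4, 12 and 16 among subjects with enthesitis (LEI > 0) at baseline".
- **PASI100.** The same log-rank list has "Time to first achievement of PASI100 among subjects with PsAID" of at least 3 at baseline. SAP 2.2.3 defines the endpoint as "Time to first achievement of PASI100 among subjects with at least 3% BSA at baseline", and SAP 2.6 agrees.
- **HADS.** Under the continuous endpoints it has "HADS change from baseline to Week 24 and 52". SAP 2.2.3 has "Depression and anxiety as assessed by change in HADS score from baseline to Weeks 16 and 52", and SAP 2.6 gives the same two visits.

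The protocol (synopsis and Section 3) agrees with SAP 2.2.3 and 2.6 on both populations and on the HADS visits.

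**The concern.** Section 6.6.5 is the text a programmer works from. For these three endpoints it names a population or a visit that differs from the one in the definitions, so one section or the other has to be overridden. If that happens after unblinding, the choice can be questioned even when it is the obvious one. If 6.6.5 is followed literally, the enthesitis analysis has no meaning, the PASI100 analysis is run in the wrong subjects, and a HADS table is produced at a visit where the instrument is not given.

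**Working it through.** The plan states no figure on this point, so the check sets the texts side by side.

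| Analysis | SAP 6.6.5 | Definition | Where defined |
|---|---|---|---|
| Time to enthesitis resolution | baseline LEI = 0 (also 6.6.6) | baseline LEI > 0 | SAP 2.2.3, 2.6, 3.2.2; protocol synopsis and Section 3 |
| Time to first PASI100 | baseline PsAID ≥ 3 | baseline BSA ≥ 3% | SAP 2.2.3, 2.6; protocol synopsis and Section 3 |
| HADS change | Weeks 24 and 52 | Weeks 16 and 52 | SAP 2.2.3, 2.6; protocol synopsis and Section 3 |

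**Enthesitis.** The event is LEI = 0. If the population is also LEI = 0 at baseline, every subject meets the event at time zero and there is no time to analyse. If the words saying that subjects have enthesitis are held to as well, the population is empty, because LEI cannot be both zero and above zero. Either way the four LEI subgroups listed in 6.6.6 contain nobody. SAP 3.2.2 states the reason for the restriction to LEI > 0: "to ensure this represents improvement in enthesitis rather than having no enthesitis at baseline".

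**PASI100.** Compare the two conditions over the four combinations of baseline status.

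1. BSA ≥ 3% and PsAID ≥ 3: included under both.
2. BSA ≥ 3% and PsAID < 3: belongs to the endpoint but is excluded by 6.6.5.
3. BSA < 3% and PsAID ≥ 3: not part of the endpoint but admitted by 6.6.5.
4. BSA < 3% and PsAID < 3: excluded under both.

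Protocol 8.1.3.3 says that once treatment has started, PASI is assessed only in subjects with at least 3% BSA at baseline. Subjects in row 3 therefore have no post-baseline PASI. The 6.6.5 rule censors non-achievers at their last derivable assessment, which for them is baseline at the latest. They leave the risk set before the first post-baseline visit and add nothing to the log-rank test. The material error is row 2, where subjects with usable data are lost. The PASI90 bullet in the same list correctly uses BSA ≥ 3%, so the two skin-response curves would describe different populations.

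**HADS.** The Schedule of Activities marks HADS at Day 1, Week 16 and End of Treatment only. Week 16 is the one post-baseline HADS visit before placebo subjects start izokibep. For Week 24, SAP 5.1.4 and Table 2 can map an early-termination or unscheduled visit on Days 155 to 196 to that time point; an early-termination visit qualifies only if the subject has no actual visit at or after it. Any Week 24 values would therefore come from such visits, chiefly early leavers, and not from the randomized groups as a whole.

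**The case against.** The strongest reply is that these are drafting slips which no competent programmer would follow. The enthesitis bullet contradicts itself, and the subgroups beneath its copy in 6.6.6 reveal the intent. The PsAID condition sits directly below a bullet where it belongs. Week 24 looks carried over from the HAQ-DI bullet just above. The correct definition appears at least twice elsewhere in the SAP for each item. All of this stands, and it is why the point is small. It does not make 6.6.5 right.

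A reader might infer several stronger things that the documents do not support.

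- *The placebo-controlled HADS comparison is lost.* The lead-in to the continuous list says its endpoints are analysed at Week 16 by the repeated-measures model, and SAP 2.2.3 and 2.6 name Week 16. The comparison is still planned; only the bullet omits it.
- *The Week 24 HADS table would be empty.* The windowing rule could put a few visits there. Sparse and unrepresentative is as far as one can go.
- *The PASI100 curve would be distorted by subjects without PASI data.* Those subjects are censored at about baseline. The harm is the exclusion of eligible subjects.
- *Most of the trial could enter the enthesitis analysis wrongly.* The 70% figure for LEI = 0 is an enrolment cap. The sample-size section expects up to 60% with enthesitis, that is at least 1 − 0.60 = 40% without. On about 325 subjects these figures give 0.40 × 325 = 130 and 0.70 × 325 = 227.5, but only under a reading that makes every such subject an event at time zero, which would be noticed at once.

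**Conclusion.** The three entries in SAP 6.6.5, and the repeat of the enthesitis entry in 6.6.6, are wrong as written. They are internal inconsistencies, and nothing suggests that anyone chose these populations or visits on purpose. Read literally, one analysis is degenerate, one drops eligible subjects, and one names a visit without scheduled data.

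The consequence is minor. All three endpoints are exploratory, and SAP 6.6.5 treats their p-values as descriptive. The primary endpoint, the secondary endpoints and the type I error rate are unaffected. The number of subjects with BSA ≥ 3% and PsAID < 3 cannot be derived, because the documents give no joint distribution of the two measures. The conclusion assumes that SAP 2.2.3 and 2.6, which agree with the protocol, state the intended definitions.

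**What to change.** - In SAP 6.6.5 and 6.6.6, give the baseline condition for time to resolution of enthesitis as LEI > 0.
- In SAP 6.6.5, give the population for time to first PASI100 as BSA ≥ 3% at baseline, matching the PASI90 bullet.
- In SAP 6.6.5, list HADS change at Weeks 16 and 52. This bullet deserves care: SAP 2.7.6 also lists HADS as a safety variable, but SAP 6.7 contains no HADS analysis, so 6.6.5 is its only specific method statement.

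The cost is a few words in the SAP, with no protocol change, no new data and no effect on sample size. The correction should be dated before unblinding; if that point has passed, record it as a correction to the definitions in 2.2.3 and 2.6.
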